Subjects will be recruited from the clinic population at the Yale Children's Diabetes Program who meet eligibility criteria. Additional subjects may be recruited from local advertising and/or the website *clinicaltrials.gov*. Potential subjects may be emailed information regarding the study, including copies of the consent forms, and if interested will be invited to the research center for formal enrollment.

d. Consent Process

The principal investigators, co-investigators, or study coordinators will introduce the studies to eligible participants and their caretakers during routine medical visits or in the form of a mailing or phone call. Prospective subjects/caretakers will have a face-to-face meeting with the investigator and/or study coordinator to address questions about the study rationale, procedures, risks and benefits. In order to identify and clarify any misconceptions, parents/caretakers will be encouraged to describe the research procedures and their associated risks in their own words, followed by correction of any errors by the investigator or study coordinator. All the subjects in the proposed studies will be minors; parent/guardian permission will be obtained for all subjects; additionally, for subjects age 7 or older, subject assent will also be obtained, as per Yale IRB guidelines. The parents/caretakers of participants will be encouraged to ask questions and will be clearly informed about the time required for these studies and their rights of non-participation and/or withdrawal. Caretakers/parents will be given copies of the signed consents to keep. Since personal health information will be collected as part of this research protocol, parents/caretakers will also be asked for authorization to collect this information in accordance with HIPAA and Yale IRB guidelines.

e. Sample Size

We will enroll a convenience sample of 24-48 subjects (8-16 in each of the three age cohorts), the final number depending on whether additional cohorts needed to be repeated at any given age group. There is no formal sample size calculation for this study.

5. Study Procedures

The study will consist of two visits, separated by no more than two weeks: an enrollment visit and a hotel visit.

a. Enrollment Visit

Subjects and parents/caregivers invited to participate in the study will undergo the consent process as described above, and then have the following study procedures:

1) Medical History

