Automated Insulin Delivery Device Acceptance	INSPIRE AID Acceptance (Draft) – Teen
PARENT OF YOUTH W T1D SURVEYS	
Fear of hypoglycemia	Hypoglycemia Fear Survey – Parent version
Diabetes burnout/burden	Problem Areas in Diabetes – Parent version
Quality of life–diabetes specific	Pediatric QoL Inventory (PedsQL) – Diabetes Module (8-12)– Parent version
Quality of life–diabetes specific	Pediatric QoL Inventory (PedsQL) – Diabetes Module (13-18) – Parent version

CONSTRUCT:	MEASURE:
Automated Insulin Delivery Device Acceptance	INSPIRE AID Acceptance (Draft) – Parent Version
ALL AGES	
Technology Acceptance	Comfort and Use of Technology Survey
Glucose Monitoring Satisfaction	The Glucose Monitoring Satisfaction Survey (GMSS)

6. Data Analysis

a. Primary Endpoint

The primary endpoint for the short-duration hotel study is safety, as defined as: 1) no more than one confirmed $BG < 50$ mg/dL; 2) no more than two confirmed $BG \geq 300$ mg/dL longer than 2 hours, unless determined to be from an infusion site failure; 3) no $BG \geq 400$ mg/dL; 4) no blood ketone level > 1.0 mmol/l for longer than 2 hours, or any ketone level > 3.0 mmol/L, unless determined to be from an infusion site failure; and 5) no significant adverse events, such as severe hypoglycemia (seizure, loss of consciousness), diabetic ketoacidosis.

b. Secondary Endpoints

Efficacy endpoints of interest will include:

- a. Mean meter and sensor glucose
- b. % Time in range (70-180 mg/dL)
- c. % Time below range (<70 mg/dL)
- d. % Time above range (>180 mg/dL)
- e. % Time in hypoglycemia (<60 mg/dL)
- f. % Time in hyperglycemia (>250 mg/dL)
- g. % time AP system active

The glycemic metrics will be calculated by total 24-hour period, and also broken down into daytime (6AM-11PM) and nighttime (11PM-6AM) periods.

c. Stopping

If an individual subject has two episodes of a confirmed $BG < 50$ mg/dL (separated by at least 30 minutes), blood ketones > 1.0 mmol/L for over 2 hours, or any blood ketone level > 3.0 mmol/L, then the study will be stopped for that subject. If any subject has a seizure, loss of consciousness or ketoacidosis ($CO_2 < 15$ mEq/L, or $pH < 7.3$) the study will be stopped for that subject and no additional subjects will be enrolled until the DSMB reviews the data.

d. Continuation

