If stopping criteria are NOT met for an age cohort, then after that cohort is completed we will proceed to next lower age cohort after DSMB review and approval. However, even if stopping criteria are not met, additional cohorts at a given age range may be enrolled at discretion of investigators if adjustments to algorithm tuning parameters are desired based on glycemic results and comparison with subjects' pre-study baseline glycemic profiles.

7. Financial Considerations

a. Subject compensation

Subjects/parents will receive \$50 for the enrollment visit and \$100/day for the hotel visit, for a maximum of \$350 compensation for participation.

b. Meal Stipend

All subject meals during the hotel stay will be covered by the study. Parents will receive \$75 per day stipend for their meals and expenses during the hotel stay. Parking at the hotel will be covered by the study.

8. Adverse Event Reporting and Safety Monitoring

a. Definition

Reportable adverse events in this study include any untoward medical occurrence that meets criteria for a serious adverse event or any medical occurrence (expected or unexpected) in a study participant that is study or device-related.

Hypoglycemic events are recorded as adverse events if the event required assistance of another person due to altered consciousness and required another person to actively administer carbohydrate, glucagon, or other resuscitative actions to prevent harm. This means that the subject was impaired cognitively to the point that he/she was unable to treat his or herself, was unable to verbalize his or her needs, was incoherent, disoriented, and/or combative, or experienced seizure or coma. These episodes may be associated with sufficient neuroglycopenia to induce seizure or coma. If glucose measurements are not available during such an event, neurological recovery attributable to the restoration of glucose to normal is considered sufficient evidence that the event was induced by a low plasma glucose concentration.

Hyperglycemic events are recorded as adverse events if the event involved diabetic ketoacidosis, as defined by the DCCT, and had all of the following:

- Symptoms such as polyuria, polydipsia, nausea, or vomiting;
- Serum ketones or large/moderate urine ketones;

- Either arterial blood pH <7.30 or venous pH <7.24 or serum bicarbonate <15; and
- Treatment provided in a health care facility

b. Recording of adverse events

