Throughout the course of the study, all efforts will be made to remain alert to possible adverse events or untoward findings. The first concern will be the safety of the participant, and appropriate medical intervention will be made. The study investigator will assess the relationship of any adverse event to be related or unrelated by determining if there is reasonable possibility that the adverse event may have been caused by the study device or study procedures.

The intensity of adverse events will be rated on a three-point scale: mild, moderate, or severe. It is emphasized that the term severe is a measure of intensity: thus a severe adverse event is not necessarily serious. For example, itching for several days may be rated as severe, but may not be clinically serious.

Adverse events that continue after the participant's discontinuation or completion of the study will be followed until their medical outcome is determined or until no further change in the condition is expected.

c. Reporting serious or unexpected device-related events

A serious adverse event is any untoward occurrence that:

- Results in death
- Is life-threatening; (a non life-threatening event which, had it been more severe, might have become life-threatening, is not necessarily considered a serious adverse event)
- Requires inpatient hospitalization or prolongation of existing hospitalization
- Results in significant disability/incapacity
- Is a congenital anomaly/birth defect

d. Unanticipated adverse device event

An unanticipated adverse device event is defined as an adverse event caused by, or associated with, a device, if that effect or problem was not previously identified in nature, severity, or degree of incidence.

Serious or unexpected adverse events must be reported to the PI immediately. The PI will notify the Yale IRB, DMSB, FDA, and device manufacturer of any adverse device event that is both serious and unexpected. Notification will be made within 5 days after the PI becomes aware of the event, as per Yale IRB requirements.

e. Data Safety Monitoring Board (DSMB)

Drs. [name] and [name] will convene a Data Safety Monitoring Board, (DSMB), comprised of independent clinicians experienced in the management of young children with type 1 diabetes, to review study protocols and safety reports with study

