investigators. The DSMB will be responsible for oversight of the proposed protocol. The DSMB will monitor the ongoing safety of the studies through periodic reports, at least twice a year, provided by the clinical center, and any adverse event reports as described above requiring notification will also include the Chair of the DSMB. The DSMB will meet with Drs. [name] and [name] every six months, either in person or by conference call, to review study progress and adverse events. In addition, the DSMB will meet with study investigators before the initiation of successively younger subject cohorts, for their input on safety, before any subjects are enrolled, in order to approve the monitoring plans for each study phase at their start.

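### At the same age, no number of individual BG <50 mg/dL or ketone stops requires prompt DSMB notice or DSMB review before more children start closed loop

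*Combined protocol and SAP*

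**What the plan says.** **Individual stops.** Under 5.b.7, repeated in 6.c, a child stops after two confirmed BG episodes below 50 mg/dL at least 30 minutes apart, ketones that stay above 1.0 mmol/L beyond 2 hours, "or any blood ketone level > 3.0 mmol/L, then the study will be stopped for that subject". Table 1 (5.b.8) adds rows that end the study for a child on clinical grounds, such as inability to take oral treatment, or vomiting.

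**Hold.** Ketoacidosis, a seizure or loss of consciousness in any child also means that "no additional subjects will be enrolled until the DSMB reviews the data". No other event in these sections has that effect.

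**Moving on.** Section 6.d: "If stopping criteria are NOT met for an age cohort, then after that cohort is completed we will proceed to next lower age cohort". That step first needs the DSMB's review and approval. The section adds that "even if stopping criteria are not met, additional cohorts at a given age range may be enrolled at discretion of investigators" when retuning of the algorithm is wanted. Section 3 likewise makes younger cohorts conditional on no stopping criteria having been met. Section 4.e allows 8-16 children per age, "the final number depending on whether additional cohorts needed to be repeated at any given age group".

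**Notice to the DSMB.** Section 8.d: "The PI will notify the Yale IRB, DMSB, FDA, and device manufacturer of any adverse device event that is both serious and unexpected", within 5 days. Section 8.e: "any adverse event reports as described above requiring notification will also include the Chair of the DSMB". Otherwise the DSMB receives reports at least twice a year and meets the investigators before each younger cohort.

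**Endpoint.** Safety is primary (6.a). Item 1 allows at most one confirmed BG below 50 mg/dL. Item 4 excludes the same ketone levels, "unless determined to be from an infusion site failure".

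**The concern.** Read per child, a stop for two BG episodes below 50 mg/dL is a failure of endpoint item 1, and a ketone stop not caused by site failure is a failure of item 4. Several such failures in one group are what an independent board should see before more children of that age are exposed, particularly if the algorithm has been retuned in between. The plan makes the DSMB the gatekeeper for each step down in age, but gives it no required role between groups of the same age.

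For children under 8 there is no younger cohort, so no step-down review follows. In that group pre-meal boluses may also be withheld at the investigator's discretion (5.b.4).

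Two related gaps make this worse. Section 6.d covers only the case where stopping criteria are not met, without saying whether an individual stop counts as meeting them. And the one event-driven hold refers to enrollment, which takes place at a visit about 1-2 weeks before closed loop begins.

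**Working it through.** **1. The plan's own figure.** 3 cohorts × 8 = 24 and 3 × 16 = 48, which agrees with the 24-48 in 4.e. The plan states no stop rate, acceptable rate, cohort-level threshold or start schedule, so there is no further figure to reproduce.

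**2. Routes by which a BG <50 or ketone stop could reach the DSMB before more same-age children start.**

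- *Hold in 5.b.7 and 6.c:* needs ketoacidosis, a seizure or loss of consciousness. Not triggered.
- *Five-day notice (8.d):* needs a device event that is serious as well as unexpected. BG below 50 mg/dL without altered consciousness, or ketosis without DKA, would not ordinarily qualify. The specific paragraphs of 8.a do not record either as an adverse event. The opening sentence of 8.a is wider (any device-related occurrence) but sets no notification time.
- *Copy to the Chair (8.e):* applies only to reports already requiring notification.
- *Step-down review (6.d, 8.e):* certain to occur before a younger cohort, but after the same-age children have been treated.
- *Twice-yearly report (8.e):* the hotel visit lasts up to 60 hours, so a repeat cohort could finish between reports.

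None requires review within an age. Eight stops in 8 children would have the same formal consequence as none.

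**3. How often it could matter.** Assume independent stops with a common rate p. For n children, P(at least 2 stops) = 1 − (1−p)^n − n·p·(1−p)^(n−1). For n = 8 and p = 0.10: 1 − 0.4305 − 0.3826 = 0.1869.

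| Assumed p | 5% | 10% | 20% | 30% |
|---|---|---|---|---|
| n = 8, at least 2 | 0.057 | 0.187 | 0.497 | 0.745 |
| n = 8, at least 3 | 0.006 | 0.038 | 0.203 | 0.448 |
| n = 4, at least 2 | 0.014 | 0.052 | 0.181 | 0.348 |
| n = 8, at least 1: 1 − (1−p)^8 | 0.34 | 0.57 | 0.83 | 0.94 |
| Expected stops in 8 (8p) | 0.4 | 0.8 | 1.6 | 2.4 |

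The n = 8 rows describe a first cohort of 8 that may be followed by a repeat of 8, the maximum of 16 per age. With a trigger of two, 8 children would be held in those cases; with two groups of four, 4 would be. Held means delayed, not necessarily spared harm. If all children of an age start together with no repeat, nobody is held.

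**4. The ambiguity in 6.d.** If one individual stop counts as a stopping criterion met, a cohort of 8 meets it with probability 34% even at a 5% rate, and the plan does not say what follows. If it does not count, no number of such stops matters. The two readings are far apart and the text does not choose between them.

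**5. Hold and start dates.** Section 5 puts the two visits no more than two weeks apart, and 5.b places the hotel visit about 1-2 weeks after enrollment. A child who has attended the enrollment visit is already enrolled, so a ban on further enrollment does not expressly stop that child from starting.

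**The case against.** The strongest reply is that the plan is better guarded than this suggests. On-site staff, SMS alerts, midnight checks and individual stops protect each child. Investigators may pause voluntarily. The DSMB approves a monitoring plan for each phase (8.e); that plan is not shown and could contain a count trigger. Read literally, 6.d and section 3 might make one stop enough to block the younger cohort, which is stricter than a trigger of two. All of this stands, and it keeps the priority down. It does not supply a required same-age review in the text available.

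A reader might infer that children in a younger cohort could start after several stops without independent review. The documents rule that out: DSMB review and approval come first, whatever the number of stops. Nor is it true that no individual stop leads to review, since ketoacidosis, a seizure or loss of consciousness does.

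A reader might also infer that 6.d expressly allows a repeat cohort after stopping criteria have been met. Its discretion sentence addresses the case where they have not been met. Its wording suggests that repeats may also follow when they have, but it states no conditions. That is silence, not permission.

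Finally, repeats are contingent under 4.e, groups of four appear nowhere, and the stop rates are assumed. The range of 6% to 74% shows how the result depends on the rate; it is not an estimate for this trial.

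**Conclusion.** The point holds for children of the same age. Within an age cohort, or before a repeat at that age, no number of BG <50 mg/dL or ketone stops requires prompt DSMB notice or review. Section 6.d leaves open whether such stops count against a cohort and what follows at the same age, and the existing hold does not expressly reach children already enrolled.

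Under the text shown, the chance that these stops alone require a same-age review is zero. How often that matters rests on independent stops, an assumed rate, and a second group or repeat actually taking place. The hold-wording gap is separate: it matters whenever enrolled children are waiting to start at the time of a serious event.

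Priority is low to moderate. The gain is earlier independent review, and the documents do not support a claim that harm would be reduced by any stated amount.

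**What to change.** 1. In 5.b.7 and 6.c, send every individual stop, including those from the Table 1 rows that end the study for a child, to the DSMB Chair when it occurs, with the investigator's view on site failure.
2. In 6.d, state whether individual stops count as cohort stopping criteria. Require DSMB review before any further group or repeat cohort of that age starts closed loop once a set number of stops is reached. The DSMB should set the number in its phase monitoring plan (8.e) and say how site-failure and Table 1 symptom stops are counted. Two in a cohort of 8 is an example only.
3. Define the hold after ketoacidosis, a seizure or loss of consciousness as no new closed-loop starts until DSMB review, not only no new enrollment.

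Individual thresholds stay as they are.

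**Cost.** A short amendment, about 0.4 to 2.4 notices per 8 children at rates of 5% to 30% (Table 1 symptom stops would add to this), and an occasional ad hoc DSMB call. Some pauses will be due to chance. With a trigger of two in 8, a repeat would be held in 6% of cases at a 5% rate and 19% at 10%; with three, in 1% and 4%. Whether those pauses are needless depends on an acceptable rate that the plan does not give, which is why the DSMB should choose. The two-week limit between visits should be extendable for held children.

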Approximately 1-2 weeks after the enrollment visit, subjects and at least one parent/guardian will return for a "hotel" visit, of up to 60 hours, during which time the following will occur:

1) Initiation of Closed-Loop

Subjects will return to study site in the morning of the day of admission, for review of interim diabetes control and uploading of pump, meter and CGM data. Subjects' current

insulin pumps and sensors will be swapped for the study pump and sensor, and the system will be initialized and activated under study staff supervision. Study subjects will be trained on proper use of the system and will receive hard-copy training materials to use as reference. Before leaving the study facility, subjects will be required to demonstrate competency with basic system operations, and successful operation of the SMS alert system for subjects' and staff cell phones will be ensured. This training portion of the study may occur at the Yale Children's Diabetes Research Program facility or at a conference room at the study hotel.

2) Activities During Hotel Visit

Subjects will be encouraged to participate in usual daily activities, including exercise, eating out, shopping, etc) as long as they remain within a 15-minute walking radius of the study site, and they have a functioning cell phone with messaging capabilities. There will be age-appropriate scheduled activities with the study group as well as personal "down-time." During the entire duration of this phase, subjects will be under direct supervision of a parent or study staff member at all times. Subjects and parents will be required to return to hotel by 9 pm and have BG level checked at midnight each night they are at the hotel. A member of the study staff will be available at the hotel each night during the study to ensure subject safety and will check subjects' BG levels at midnight each night.

3) Exercise

Subjects will be encouraged to participate in exercise activities each day during the hotel visit, such as walking, jogging, exercise room, or sports. Exercise will not be announced to the controller, but subjects that usually pre-treat exercise with small amounts of carbohydrate may continue to do so after discussion with study staff. All subjects will check BG levels prior to and after the planned exercise.

4) Diabetes Management During Hotel Visit

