If an individual subject has two episodes of a confirmed $BG < 50$ mg/dL (separated by at least 30 minutes), blood ketones > 1.0 mmol/L for over 2 hours, or any blood ketone level > 3.0 mmol/L, then the study will be stopped for that subject. Recall that subject will test for ketones after a confirmed $BG \geq 300$ mg/dL following CGM readings ≥ 300 mg/dL for > 1 hour. If any subject has a seizure, loss of consciousness or ketoacidosis ($CO_2 < 15$ mEq/L, or $pH < 7.3$) the study will be stopped for that subject and no additional subjects will be enrolled until the DSMB reviews the data.

If for any subject the $BG \geq 300$ mg/dL and blood ketones are > 1.0 mmol/L, the closed-loop control will be temporarily stopped, the infusion site will be changed, and supplemental insulin may be given at the discretion of the investigator. The closed-loop control will be restarted if $BG < 250$ mg/dL and blood ketones < 0.6 mmol/L.

If for any subject the $BG \geq 400$ mg/dL for any ketone levels, the closed-loop control will also be temporarily stopped, the infusion site will be changed, and supplemental insulin may be given if the investigator concludes that the issue is related to a site failure and not due to malfunction of the controller. The closed-loop control will be restarted if $BG < 250$ mg/dL and blood ketones < 0.6 mmol/L.

Additional information is shown in the Treatment Protocol table.

8) Treatment Protocol Table

Table 1. Hypoglycemia and hyperglycemia monitoring and treatment procedures.

Meter BG (mg/dL)	Ketones (mmol/L)	Clinical State	Action	Monitoring
Any		Seizure, loss of consciousness, or inability to consume oral treatment	STOP system Treat with SQ glucagon Notify MD/NP End closed-loop STOP study for this patient	Repeat BG every 15 minutes until $BG \geq 70\text{mg/dL}$
<70		Conscious, well-appearing	Treat with oral glucose Notify MD/NP Repeat MBG Continue closed-loop	Repeat BG every 15 minutes until $BG \geq 70\text{mg/dL}$
70-299		Asymptomatic and well	Continue closed-loop	Check BG (Premeal, pre and post exercise and midnight)
300-399	≤ 1.0	Asymptomatic and well	Continue with closed-loop Notify MD/NP May consider supplemental insulin	Repeat BG and ketones in 1 hour
300-399	> 1.0	Asymptomatic and well	Notify MD/NP SQ insulin correction, set change Suspend closed-loop May restart if $BG 80-250\text{ mg/dL}$ and ketones $< 0.6\text{ mmol/L}$. Encourage oral fluid intake.	Repeat BG and ketones in 1 hour

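### The halt after a seizure, loss of consciousness or ketoacidosis is tied to enrolment, not to closed-loop starts, so already-enrolled children of the same age cohort could start the system before the DSMB review

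*Combined protocol and SAP*

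**What the plan says.** The halt appears twice in the same words, in section 5.b.7 (Stopping Criteria) and section 6.c (Stopping). If any subject has a seizure, loss of consciousness or ketoacidosis, that subject's participation ends and "no additional subjects will be enrolled until the DSMB reviews the data". For a seizure or loss of consciousness, Table 1 adds action for the affected child only: "STOP study for this patient".

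Enrolment is a defined step. Under section 4.c, families who have received study information "if interested will be invited to the research center for formal enrollment". Section 5 opens: "The study will consist of two visits, separated by no more than two weeks: an enrollment visit and a hotel visit". The enrolment visit (5.a) covers consent, history, examination, A1c and the fitting of a sensor for baseline data. The controller is first activated at the hotel visit (5.b), which is timed as follows: "Approximately 1-2 weeks after the enrollment visit, subjects and at least one parent/guardian will return".

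Three other provisions involve the DSMB. Section 6.d requires its approval before moving to the next lower age cohort. Section 8.e requires a meeting before each younger cohort, and reports and meetings about every six months. Section 8.d requires notification of adverse device events that are both serious and unexpected: "Notification will be made within 5 days after the PI becomes aware of the event".

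**The concern.** A trial-level halt is there so that independent reviewers can look at a serious event before more children are exposed. This one blocks a step that comes before exposure. A child wearing the baseline sensor has already been enrolled, so is not an additional subject in the sense of the rule, and nothing written holds that child's hotel visit. Staff following the text exactly could admit the remaining enrolled children of the cohort while the review is pending. The DSMB could then be reviewing an event after other minors of the same age group had been on the same controller for up to 60 hours each. Safety is the primary endpoint (6.a), so the rule should act on the start of closed loop.

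**Working it through.** No error rate, power or sample-size formula bears on this point, and section 4.e states that there is no formal sample size calculation. The check sets the provisions side by side and adds simple arithmetic.

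**What each provision stops after such an event**

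| Provision | Affected child | New enrolment visits | Hotel visits of children already enrolled, same cohort | Next age cohort |
|---|---|---|---|---|
| 5.b.7 and 6.c | stopped | stopped until DSMB review | not mentioned | no new enrolment until DSMB review |
| Table 1 | stopped | not mentioned | not mentioned | not mentioned |
| 6.d and 8.e, cohort progression | – | – | not mentioned | needs DSMB review and approval |
| 8.d, notification | – | – | not mentioned | – |

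The fourth column is empty throughout. No provision sets a deadline for the DSMB review after a halt.

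**How soon a waiting child may be due**

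Inputs: a gap of about 7 to 14 days between the visits (5 and 5.b), and notification within 5 days (8.d). If a child was enrolled d days before the event and has not yet been admitted, the hotel visit falls due between max(0, 7 − d) and 14 − d days after the event.

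- d = 0: 7 to 14 days after the event.
- d = 2: 7 − 2 = 5 to 14 − 2 = 12 days.
- d = 7: 0 to 14 − 7 = 7 days.

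So a child enrolled 2 or more days before the event may be due on or before day 5, the outer limit for notification. That limit is not the time to DSMB review, which is not stated.

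**How many children**

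Input: 8 to 16 subjects per age cohort (4.e). This agrees with the stated total: 3 × 8 = 24 and 3 × 16 = 48.

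- Children enrolled and admitted one at a time: 0 waiting.
- Whole cohort enrolled before the event (assumption): at most 8 − 1 = 7, or 16 − 1 = 15.

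The figure of 15 is an outer bound. Section 4.e links the final number to repeated cohorts. If 16 is reached by repeating a cohort of 8, and the repeat is enrolled only after the first is completed, the bound returns to 7.

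**The case against.** The strongest reply is that enrolled may be meant loosely, as put on the study system. Section 6.d speaks of whole cohorts being enrolled, and section 5.b.7 sits inside the hotel-visit section. Serious or unexpected events go to the principal investigator immediately (8.d), reports that require notification also go to the DSMB chair (8.e), and section 8.b puts the participant's safety first. An investigator could well postpone hotel visits, and nothing forbids it. This stands in part: the word is ambiguous and the intention may have been sound. But the protocol also gives enrolment a specific, earlier meaning, and no sentence requires the postponement.

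Three stronger readings are tempting, and the documents do not support them.

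- A reader might infer that this halt is the trial's only brake. It is not. Sections 3, 6.d and 8.e make progression to younger children conditional on the stopping criteria and on DSMB approval. The gap lies within one age cohort.
- A reader might infer that the two-week limit between visits drives the site to admit waiting children. The text says nothing of the kind. It only lacks a provision for a child whose visit is held.
- A reader might try to state how many children would typically be waiting. Hotel-group size, the spacing of hotel stays and the order of enrolment visits are not given, so only the range from 0 to the cohort bound can be supported.

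Nor should the 5-day notification period or the six-monthly DSMB meetings be taken as the delay to review. The halt calls for its own event-triggered review, for which no time is set.

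**Conclusion.** The point holds within an age cohort and on the literal wording. The halt acts on enrolment, closed loop starts about 1-2 weeks later, and no other provision holds the children in between. The number who could start before DSMB review runs from 0 to at most 7-15, each for up to 60 hours. The upper end assumes that a full cohort of 8-16 is enrolled before the event. Younger cohorts remain protected by the DSMB gates.

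The rule is also silent on other children in closed loop when the event occurs. That is a separate question, not included in the 0 to 15 count of children yet to start, and it is for the sponsor and DSMB to settle.

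**What to change.** Reconcile the wording in 5.b.7 and 6.c with the two-visit schedule so that the halt covers exposure: no additional subject is enrolled, and no already-enrolled subject begins the hotel visit, until the DSMB has reviewed the data. In section 5, let a subject held for this reason exceed the two-week interval, with eligibility re-confirmed before the hotel visit. The sponsor and DSMB should state in advance what applies to other subjects in closed loop at that time; no clinical rule is proposed here.

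The cost is a short amendment in two places and one sentence in section 5. If a halt occurs, some hotel visits may be rescheduled and baseline sensor data may have to be collected again.
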